6.1.2. Safety Monitoring and Stopping Rules for Abnormal Liver Chemistry Measurements

The criteria in [Table 2](#) were adapted in accordance with the non-binding recommendations contained within the Food and Drug Administration (FDA) Guidance for Industry Drug-Induced Liver Injury: Pre-marketing Clinical Evaluation, from the U.S. Department of Health and Human Services in July 2009.

Although there is no reasonable expectation that study drug exposure of ≤ 200 mg QD will result in hepatic toxicity, out of an abundance of caution in this study, abnormal transaminase results will be assessed as follows.

If stopping criteria are met at any time during the Treatment Period, study drug should be held until confirmatory testing of the transaminase, with additional measurements of total bilirubin, alkaline phosphatase, complete blood count (CBC), and international normalized ratio (INR) is performed and be reported as an adverse event of special interest (AESI). Ideally, confirmatory testing would be performed within 48-72 hours of the initial receipt of the abnormal result. Confirmation testing through the central lab is preferred, but local laboratory testing may be necessary in certain circumstances. In cases where a possible Hy's Law case is present or any

other seriousness criteria are met, this should be reported as a SAE and AESI. [Table 2](#) outlines specific stopping criteria for this study.

Table 2. Stopping Criteria and Increased Monitoring for Liver Chemistry Elevations

Criteria	Actions
Appearance of fatigue, nausea, vomiting right upper quadrant pain or tenderness, fever, jaundice, rash and/or eosinophilia (>5%) believed to be related to liver injury or hypersensitivity.	Hold study drug, measure liver chemistry (AST/ALT/ALP), total bilirubin, total bile acids, CBC with differential and INR within 48-72 hours and notify Sponsor.
ALT or AST \geq 5x ULN	Discontinue study drug and notify Sponsor. Follow the protocol's Laboratory Monitoring of Liver Function .

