ALT \geq 3x ULN	
Treatment Periods 1 and 2:
 
 
Monitor liver chemistry (AST/ALT/ALP), total bilirubin, total bile acids, CBC with differential and INR within 48-72 hours and notify Sponsor 
If no other stopping criteria are met, monitor AST/ALT/ALP and INR 2x weekly for the remainder of the current treatment period (may be performed weekly if AST/ALT stabilizes and the subject is asymptomatic) while continuing study drug 
If ALT $>3x$ ULN at the conclusion of the current treatment period, withdraw the subject from the study 
Treatment Period 3:
 
 
Follow the same notification and monitoring instructions detailed in (a) and (b) above for Treatment Periods 1 and 2. 
If ALT $>3x$ ULN persists for 4 weeks, discontinue study drug and notify Sponsor

Criteria	Actions	
ALT \geq 3x ULN	AND total bilirubin \geq 2x ULN (>35% direct bilirubin) ¹	Discontinue study drug and notify Sponsor. Possible Hy's Law case— report as SAE and AESI
	AND INR >1.5	Discontinue study drug and notify Sponsor. Possible Hy's Law case— report as SAE and AESI
	AND total bile acids $>3x$ ULN	Hold study drug and notify Sponsor. Measure liver chemistry (AST/ALT/ALP), total bilirubin, total bile acids, CBC with differential and INR within 48-72 hours and discuss with Medical Monitor whether to discontinue study drug.
	AND the appearance of fatigue, nausea, vomiting right upper quadrant pain or tenderness, jaundice, fever, rash and/or eosinophilia (>5%).	Discontinue study drug and notify Sponsor.

Abbreviations: AESI, adverse event of special interest; ALP, alkaline phosphatase; ALT, alanine aminotransferase; AST, aspartate aminotransferase; CBC, complete blood count; INR, international normalized ratio; SAE, serious adverse event; ULN, upper limit of normal.

¹ If serum bilirubin fractionation is not immediately available, discontinue study drug if ALT \geq 3x ULN and bilirubin \geq 2x ULN and record the presence/absence of detectable urinary bilirubin on dipstick, which is indicative of direct bilirubin elevations suggesting liver injury.

Investigation of the underlying cause of these transaminase elevations should include, but is not limited to:

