6.1.4. Suicidality Stopping Criteria

Tildacerfont is considered to be a central nervous system (CNS)-active drug. Some CNS-active drugs may be associated with an increased risk of suicidal ideation in certain populations. Although tildacerfont has not been shown to be associated with an increased risk of suicidal ideation or behavior in past clinical studies, subjects will be monitored for such events during this study using the C-SSRS.

Individuals who answer “yes” to Question 3, 4, or 5 in the suicidal ideation section of the C-SSRS at screening or baseline are not eligible for this study. Any subject who exhibits any Suicidal Behavior or Suicidal Ideation (eg, answers “yes” to Question 3, 4, or 5 in the suicidal ideation section of the C-SSRS) will have study drug immediately discontinued and should be evaluated by a psychiatrist. This safety finding will be considered an AESI if it is not an SAE (eg, requiring hospitalization) (see [Section 7.2.8](#)).

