6.1.5. Depression or Anxiety Stopping Criteria

Any subject who develops severe depression or anxiety CTCAE Grade 3 or higher, as assessed by the Investigator, will require study drug discontinuation and appropriate follow-up. This will be considered an AESI if it is not an SAE (eg, requiring hospitalization) (see [Section 7.2.8](#)).

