If a subject develops an AE of adrenal insufficiency meeting the seriousness criteria as defined in [Section 7.2.2](#) or the event is severe in nature and in addition to suspending administration of study medication, the Investigator may consider treatment with glucocorticoid therapy. The route, type and dose of glucocorticoid treatment as well as the duration of therapy are at the discretion of the Investigator and should be in accordance with the local treatment guidelines for the treatment of adrenal insufficiency.

If a subject develops an adrenal insufficiency AE meeting the seriousness criteria as defined in [Section 7.2.2](#) or the event is severe in nature, regardless of the outcome of the serum cortisol measurement, study drug should be permanently discontinued, and the subject should undergo the Early Termination Visit.

All serious or non-serious AEs of adrenal insufficiency are considered AESI.

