7.2.8. Adverse Events of Special Interest

AESIs are those AEs (independent of seriousness criteria) that are of specific concern to this study and for which ongoing monitoring and communication with the Investigator and Sponsor may be appropriate. These events will be reported on the SAE Report Form, allowing for the collection of additional information, as warranted. The following may be considered AESIs for this study:

- Significant liver chemistry changes that do not satisfy study drug stopping rules (see [Section 6.1.2](#)). Cases of Hy's Law should also be reported as an AESI and an SAE.
- Suicidality as indicated by "yes" response to questions 3, 4, or 5 on the C-SSRS (see [Section 6.1.4](#) regarding study drug stopping criteria for suicidality).
- Depression or anxiety that is moderate or severe (CTCAE Grade 2 or higher), as assessed by the Investigator (see [Section 6.1.5](#) regarding study drug stopping criteria for depression or anxiety). This will be reported as an AESI and if seriousness criteria are met, reported as an SAE.
- Adrenal insufficiency

Adverse events of adrenal insufficiency are considered AESIs (see [Section 6.1.6](#)). Both the AE/SAE CRF and Adrenal Insufficiency CRF should be completed. Symptoms of adrenal insufficiency will be reported as an SAE if they necessitate parental glucocorticoid administration by a health care professional and two of the following criteria are met: hypotensive (systolic blood pressure <100 mmHg); nausea or vomiting; severe fatigue; documented hyponatremia, hyperkalemia, or hypoglycemia.

If hospitalization was required or the event of adrenal insufficiency is deemed to be an important medical event, life-threatening, results in a persistent or significant disability/incapacity or death, the adverse event should also be reported as an SAE.

- For SAEs of adrenal insufficiency, records from the office of health care provider, emergency facility or hospital should be obtained as source documents to provide the

following information, in addition to completing the Adrenal Insufficiency CRF and the AE/SAE CRF:

- What type, dose and route of glucocorticoid was administered and the duration of administration?
- What concomitant medications were administered?
- What clinical laboratory results are available?
- What AEs occurred?
- What was deemed to be the inciting factor leading to adrenal crisis?

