9.3.16 Adverse Events

AEs are those AEs with onset date from the signing of the ICF until the end of the follow up period.

Treatment-emergent adverse events (TEAEs) are defined as any AEs, regardless of relationship to study drug, that have an onset or worsening in severity on or after the first dose of study drug until 30 days after the final dose of study drug (Follow-up visit). For AEs that occur on the date of the first dose of study drug, the time of onset (before or after intake of study drug) will be specified and used for comparison.

If a subject discontinues study drug but remains in the study, AEs with onset date after 30 days of last dose of study drug until the end of the follow up period will be considered post-treatment adverse events.

Related TEAEs are those reported by investigators as possibly related, probably related, or definitely related to the study drug.

AESIs are events that do not meet SAE criteria but must be monitored on an ongoing basis as defined in Protocol [Section 7.2.8](#) and identified in the AE eCRF page.

Serious AEs (SAEs) are defined in Protocol [Section 7.2.6](#) and identified in the AE eCRF page.

Dose-limiting toxicities are defined as a Common Terminology Criteria for Adverse Events (CTCAE) Grade 3 or higher TEAE that is also considered at least possibly related to study drug.

Suspected unexpected serious adverse reactions (SUSARs) is an AE that is serious, related to study drug, and is not expected in the targeted disease (PCOS).

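### Two minor SAP safety-reporting corrections: the AESI definition in SAP 9.3.16 excludes serious events against the protocol section it cites, and SAP 14.3 names neither blood pressure nor vital-sign categories

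*SAP*

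**What the plan says.** **AESIs.** SAP 9.3.16: "AESIs are events that do not meet SAE criteria but must be monitored on an ongoing basis as defined in Protocol" Section 7.2.8. The sentence ends by adding that these events are identified on the AE eCRF page. The cited protocol section reads: "AESIs are those AEs (independent of seriousness criteria) that are of specific concern to this study". On depression or anxiety it adds: "This will be reported as an AESI and if seriousness criteria are met, reported as an SAE". Elsewhere in the protocol:

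- Section 6.1.2, on possible Hy's Law cases or where any "other seriousness criteria are met, this should be reported as a SAE and AESI"; the Hy's Law rows of Table 2 tell sites to "report as SAE and AESI".
- Section 6.1.6: "All serious or non-serious AEs of adrenal insufficiency are considered AESI".
- Section 6.1.4, on suicidality: "This safety finding will be considered an AESI if it is not an SAE".
- Section 6.1.5, on severe depression or anxiety: "This will be considered an AESI if it is not an SAE".

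SAP 14.1 plans a separate AESI listing. Its overall TEAE summary has no row labelled AESI.

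**Vital signs.** Protocol 7.1.2 and SAP 5.2.3.3 both include systolic and diastolic blood pressure, and SAP 5.2.3.3 also counts weight. Protocol 8.3.5.4 asks for observed values, changes from baseline, and counts and percentages within defined categories. SAP 14.3 gives descriptive statistics for pulse rate, respiratory rate and temperature, and a listing of all vital signs.

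**The concern.** The SAP narrows a definition while citing the protocol section that says the opposite. SAP section 4 makes the SAP govern where the two documents differ on planned analyses, so a programmer cannot simply fall back on the protocol. Followed literally, the AESI listing that Protocol 8.3.5.2 asks for would omit the serious cases.

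For vital signs, a literal reading of SAP 14.3 leaves blood pressure and weight in a subject listing only, with no summary by treatment group and visit and no counts of subjects in any category. Protocol 6.1.6 associates hypotension and weight loss with adrenal insufficiency, which is an AESI with its own stopping criteria, so these are not incidental measurements here. SAP section 15 declares neither difference as a change from the protocol.

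**Working it through.** No power, alpha or sample-size figure is involved; the check is a comparison of text.

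**Step 1: can an event be both AESI and SAE?**

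| Place | Answer |
|---|---|
| Protocol 7.2.8, general definition | Yes |
| Protocol 7.2.8, Hy's Law; depression or anxiety | Yes |
| Protocol 6.1.2 and Table 2 | Yes |
| Protocol 6.1.6, adrenal insufficiency | Yes |
| Protocol 6.1.4, suicidality | No |
| Protocol 6.1.5, severe depression or anxiety | No |
| SAP 9.3.16 | No, for every category |

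The SAP contradicts the definition it cites. The protocol is not uniform either: 6.1.4 and 6.1.5 conflict with 7.2.8 on seriousness.

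**Step 2: a second protocol conflict.** Section 6.1.2 has liver events that meet stopping criteria reported as AESIs. Section 7.2.8 describes the liver AESI as a significant change that does not meet the stopping rules, and then adds Hy's Law cases. A liver event that meets a stopping rule but is not a Hy's Law case is therefore an AESI under one section and not under the other.

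**Step 3: apply SAP 9.3.16 to a serious event flagged as an AESI.** The seriousness condition excludes it; the eCRF condition includes it. The sentence gives two answers. If the first is applied, the event leaves the AESI listing.

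**Step 4: where would that event still appear?**

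- Any category: the SAE listing and the listing of all AEs (SAP 14.1).
- Adrenal insufficiency: its own listing and its own row in the overall TEAE summary (SAP 14.1).
- Liver: subjects meeting Hy's law criteria are identified and listed (SAP 14.2).
- Suicidality: C-SSRS responses are listed by subject and visit (SAP 14.5).
- Depression or anxiety: no other dedicated output.

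**Step 5: vital signs.** SAP 5.2.3.3 lists six measures: systolic pressure, diastolic pressure, pulse, respiration, temperature and weight. SAP 14.3 names three for summary, so 6 − 3 = 3 are not named (systolic, diastolic, weight). Against the five in Protocol 7.1.2, 5 − 3 = 2 are not named.

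**Step 6: do the defaults fill the gap?** SAP 9.1 gives an 8-point summary for all other continuous variables unless specified otherwise, and the opening of SAP 14 presents descriptive statistics by treatment group and dose level. These might be read to cover blood pressure and weight, although the specific list in 14.3 points the other way. They cannot supply categories, and no vital-sign category is stated anywhere in the SAP.

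**The case against.** The strongest reply is that little changes in practice. The SAP sentence itself points to the eCRF, so a programmer working from the AESI flag would keep serious events. Steps 4 and 6 show that most of the information appears elsewhere, and the mock shells mentioned in SAP section 9, which are not among the documents, may already include blood pressure. The exclusion also has some footing in Protocol 6.1.4 and 6.1.5. All of this stands and is why the point is minor. It does not remove the contradiction within the SAP sentence. The flag may also be incomplete, because a site following 6.1.4 or 6.1.5 could leave it blank for a serious event.

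Several stronger readings are tempting and are not supported:

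- A reader might infer that serious AESIs vanish from safety reporting. They remain in the SAE and all-AE listings.
- A reader might infer that the study stopping rule on drug-related AESIs would be miscounted. Protocol 6.1.9 gives that rule to an unblinded Medical Monitor and does not run it from the SAP definition.
- A reader might take the ECG thresholds in SAP Table 5 as proof that vital signs were overlooked. Table 5 covers heart rate, QRS and QTcF, three of the five parameters in Protocol 8.3.5.5, so it is not a clean contrast.
- A reader might take the systolic levels in Protocol 6.1.6 and 7.2.8 as ready-made categories. One illustrates an associated sign and the other belongs to an SAE reporting criterion. Section 6.1.6 also warns that many such findings are nonspecific and common without adrenal insufficiency.

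**Conclusion.** Both corrections hold, at minor severity.

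For AESIs, the definition in SAP 9.3.16 is wrong against its cited source. The exposure is one listing, and only if the seriousness condition is applied over the eCRF flag. Serious depression or anxiety is the category for which the AESI listing matters most, since it has no other dedicated output.

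For vital signs, it is certain that SAP 14.3 does not name blood pressure or weight and that the SAP states no categories for the counts and percentages in Protocol 8.3.5.4. Whether the continuous summaries would really be missing depends on how the SAP 9.1 default is read and on the mock shells. Nothing supports saying that blood pressure goes unreported, because SAP 14.3 lists all vital signs. SAP section 15 records that the study was discontinued early with a small sample, so these summaries would be descriptive.

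**What to change.** **AESIs**

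1. Delete from SAP 9.3.16 the clause that excludes events meeting SAE criteria. Keep the reference to Protocol 7.2.8 and to the eCRF page.
2. Build the AESI listing from the eCRF AESI flag, do not exclude serious events, and add a seriousness column. The column also keeps AESIs and SAEs distinguishable, as Protocol 7.2.6 requires.
3. The sponsor must reconcile the protocol passages: 6.1.4 and 6.1.5 against 7.2.8 on seriousness, and 6.1.2 against 7.2.8 on liver events that meet stopping criteria. For the analysis, a SAP clarification or note to file is enough.
4. Before lock, check SAEs in these categories against the AESI flag.

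**Vital signs**

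Check the mock shells. Then add systolic and diastolic blood pressure and weight to SAP 14.3, as observed values and change from baseline by treatment group, dose level and visit. Have the sponsor state the categories for the counts and percentages. Otherwise, declare the omission in section 15.

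**Cost**

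A few SAP sentences, one listing column, a small table and a short pre-lock check, all from data already collected. Serious AESIs will then appear in both the AESI and SAE listings, so the two must not be added together.

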7.2.6. Serious Adverse Event Reporting

Throughout the study, the Investigator is to report all SAEs, regardless of suspected causality, to the Sponsor within 24 hours of learning of its occurrence using the SAE Report Form. AESIs (see [Section 7.2.8](#)) will also be reported in the electronic data capture (EDC) system and on the SAE Report Form and must be clearly differentiated from SAEs. Completion guidelines are provided in the Investigator Site File. The Investigator must assess and record the relationship of each event to study drug. Any SAE experienced after the follow-up period should be reported to the Sponsor only if the Investigator suspects a causal relationship to the study drug.

Recurrent episodes, complications, or progression of the initial SAE, regardless of when they occur, must be reported as follow-up to the original episode within 24 hours of the Investigator receiving the follow-up information. Follow-up information will also be captured in the EDC system and should describe whether the event resolved or continues, if and how it was treated, and whether the subject continued or withdrew from study participation. An SAE occurring at a different time interval or otherwise considered completely unrelated to a previously reported SAE should be reported separately as a new event.

The Sponsor will ensure that all suspected unexpected serious adverse reactions (SUSARs), determined based on the Reference Safety Information in the most recent version of the IB at the time of the event, will be reported to the FDA and to all Institutional Review Boards (IRBs)/Ethics Committees (ECs) overseeing the conduct of the study, in accordance with FDA 21 CFR 312.32.

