4 PURPOSE OF THE ANALYSIS PLAN

This statistical analysis plan (SAP) pre-specifies the statistical analysis methods for supporting the completion of topline results and an abbreviated clinical study report (CSR) of Study SPR001-210 for tildacerfont, an investigational drug candidate designed to treat polycystic ovary syndrome (PCOS). This SAP will be used to analyze the safety and efficacy data collected during the study. Dose-exposure-response analyses combining data across multiple studies will be conducted using a separate pharmacokinetics SAP. The planned analyses identified in this SAP may be included in regulatory submissions and/or future manuscripts.

The analysis methods described in this plan are considered *a priori*, in that they have been defined prior to clinical database freeze and treatment un-blinding. Exploratory analyses that are not defined in this SAP may be performed to support the clinical development program. Any post-hoc or unplanned analyses that are performed for the CSR, but not defined in this SAP, will be documented in the CSR. Changes from the planned analyses stated in the study protocol are described in [Section 15](#). Should the SAP and the protocol be inconsistent with respect to any further planned analyses, the language of the SAP is governing.

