10.3.2 Handling of Safety Data

10.3.2.1 Adverse Events

If the time of onset (before or after intake of study drug) cannot be determined whether an AE is treatment-emergent because of a partial onset date, the event will be counted as a TEAE.

Adverse events with incomplete start dates will be considered TEAEs, if:

- Day and month are missing and the year is equal to or after the year of the first date of study drug dosing;
- Month is missing and the year is after the year of the first date of study drug dosing;
- Day is missing and the year is equal to the year of the first date of study drug dosing and the month is equal to or after the month of the first date of study drug dosing; or
- Year is missing.

If severity or relationship of an AE to study drug is not recorded, the severity or relationship will be imputed as “severe” or relationship as “possibly related,” for analysis purposes. All efforts will be made to ensure no missing severity or relationship of an AE to study drug prior to database lock finalization.

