14.1 Adverse Events

All AE verbatim terms reported on the eCRFs will be coded using the Medical Dictionary for Regulatory Activities (MedDRA® version 24.1).

All reported AEs (including non-TEAEs) will be listed. Separate listings will be provided for SAEs, TEAEs leading to study drug discontinuation, DLTs, AESIs, SUSARS, AEs related to adrenal insufficiency, and AEs related to COVID-19.

For all TEAE tables, counting will be by subject and not by event. Additionally, if a subject reported the same TEAE on multiple occasions, the highest severity (severe > moderate > mild) or study drug relationship (related > probable > possible > unlikely > unrelated) recorded for the event will be summarized. All TEAE summary tables will present the number and percentages of subjects reporting TEAEs, unless otherwise specified. A summary of TEAEs by severity, seriousness, and relation to study drug will be tabulated.

An overall summary of TEAEs will be presented. The overall summary will include the number and percentage of subjects experiencing any AEs, TEAEs, study drug related TEAEs, TEAEs by maximum severity (highest toxicity grade), SAEs, study drug related SAEs, DLTs, SUSARs, TEAEs of adrenal insufficiency, TEAEs leading to study drug discontinuation, and deaths.

The number and percentage of subjects experiencing each TEAE, study drug related TEAE, and SAEs will be summarized by treatment group according to system organ class and preferred term. An additional table including only preferred term summarized by treatment for the number and percentage of subjects experiencing each TEAE will be presented as well.

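### The SAP judges whether a SUSAR is unexpected against PCOS, while the protocol judges it against the Investigator's Brochure, so the SUSAR listing and count can differ from what was reported

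*SAP*

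**What the plan says.** On SUSARs, SAP 9.3.16 states that such an event "is an AE that is serious, related to study drug, and is not expected in the targeted disease (PCOS". Protocol 7.2.6 makes the sponsor responsible for reporting SUSARs to the FDA and the review boards, with SUSAR status "determined based on the Reference Safety Information in the most recent version of the IB at the time of the event". The SAP definition feeds two outputs in SAP 14.1. One is a listing: "Separate listings will be provided for SAEs, TEAEs leading to study drug discontinuation, DLTs, AESIs, SUSARS". The other is a SUSAR count in the overall TEAE summary. SAP section 4 settles conflicts this way: "Should the SAP and the protocol be inconsistent with respect to any further planned analyses, the language of the SAP is governing". SAP section 15, which records departures from the protocol's analyses, does not mention the SUSAR definition.

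On partial dates, SAP 9.3.16 defines TEAEs as AEs "that have an onset or worsening in severity on or after the first dose of study drug until 30 days after the final dose". SAP 10.3.2.1 first gives a default: where it "cannot be determined whether an AE is treatment-emergent because of a partial onset date, the event will be counted as a TEAE". It then lists four conditions under which an incomplete start date counts as treatment-emergent. The only one written for a missing day with a known month begins "Day is missing and the year is equal to the year of the first date of study drug dosing" and adds that the month must be that of first dose or later.

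**The concern.** Expectedness in the protocol is a property of the drug's reference information. In the SAP it is a property of the disease. A programmer or medical reviewer who applies the SAP sentence will classify some related serious events differently from the sponsor's safety function. The study report would then carry a SUSAR listing and count that do not match the reports already sent, and nothing in the SAP would explain the difference.

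The date list raises a smaller matter. It has no entry for an onset recorded by month and year in a later calendar year than first dose, so the list and the TEAE definition do not quite meet.

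**Working it through.** There is no stated figure to reproduce. The check sets the definitions side by side and runs partial dates through the list.

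**SUSAR definition.** Both documents require the event to be serious and related. They also agree on what related means: possibly, probably or definitely (Protocol 7.2.3.2, SAP 9.3.16). They differ only on unexpected. For a serious, related event there are four cases:

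| In the IB reference information? | Expected in PCOS? | Protocol 7.2.6 | SAP 9.3.16 |
|---|---|---|---|
| Yes | Yes | not a SUSAR | not a SUSAR |
| No | No | SUSAR | SUSAR |
| No | Yes | SUSAR | not a SUSAR |
| Yes | No | not a SUSAR | SUSAR |

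The last two rows disagree, in opposite directions. SAP count minus protocol count equals the number of events in row 4 minus the number in row 3. Equal numbers in the two rows would leave the count right and the listing wrong.

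The SAP text does not supply the protocol's answer by another route. SAP 9.3.16 says that SAEs and AESIs are identified on the AE eCRF page, but it names no source for SUSAR status. The definition is all a programmer has. The same section cites Protocol 7.2.6, but only for SAEs.

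**Partial dates.** For illustration, assume a first dose on 20 November 2022; the documents give no enrolment dates. Last dose, day 84: 20 November + 83 days = 11 February 2023. End of the TEAE window: 11 February + 30 days = 13 March 2023.

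| Recorded onset | Entry met in the list |
|---|---|
| October 2022, no day | none (correct: before first dose) |
| November or December 2022, no day | third |
| January, February or March 2023, no day | none |
| 2022 only | first |
| 2023 only | first and second |
| No year | fourth |

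So an onset recorded only as 2023 is on the list, and the more precise January 2023 is not. The list must then be read with the rest of the SAP. January 2023 is certainly after first dose and inside the window, so the 9.3.16 definition makes it a TEAE. March 2023 is certainly after first dose but may fall after 13 March; if that doubt is treated as undetermined status, the default sentence counts it.

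**The case against.** The strongest reply on SUSARs is that little depends on the wording. Expedited reporting runs under Protocol 7.2.6. SAP 14.1 separately lists all SAEs and counts drug-related SAEs, so an event missing from the SUSAR listing is still visible as a related SAE. Protocol 1.2.2 reports no drug-related SAEs to date, and SAP section 15 says that a trial planned for up to 40 subjects was stopped early. All of this stands, and it limits the consequence to one listing and one summary count. It does not reconcile the definitions, and SAP section 4 gives the SAP precedence for planned analyses.

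On dates, a reader might infer that the list removes clearly post-dose events from the TEAE tables. The documents do not support that. The four conditions say when an incomplete date counts; they do not say that every other incomplete date fails to count. SAP 9.3.16 covers the omitted case, and SAP 9.3.17.1 repeats that onset from first dose is treatment-emergent. An event is lost only if the list is coded as exhaustive.

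A reader might also try to size the gap by the share of subjects whose treatment and follow-up cross a year-end. That is not the share of events affected: an event must also start after 31 December and have its month and year recorded without a day. The documents give neither the enrolment dates nor the rate of partial dates.

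Nor is the second entry in the list redundant. The first requires both day and month to be missing. The second alone covers a known day with a missing month in a later year.

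**Conclusion.** The SUSAR definition is wrong as written. It contradicts Protocol 7.2.6 on the one element that separates a SUSAR from any other related serious event, and the change is not declared. The study report's SUSAR listing and count can be wrong in either direction, by one for each discordant event. How many there would be cannot be estimated from the documents, and it may be none. This rests on the SAP sentence being applied literally; if the sponsor's own SUSAR determinations were carried into the listing, the outputs would be right but would not follow the SAP.

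The partial-date list has a drafting gap, not a misclassification rule. It deserves a clarification because a program built from the list alone would miss these events. Neither point affects efficacy, alpha, power, expedited reporting, or the SAE and related-SAE outputs.

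**What to change.** In SAP 9.3.16, replace the SUSAR sentence with the Protocol 7.2.6 rule: a serious event assessed as related to study drug and unexpected according to the IB Reference Safety Information in force when the event occurred.

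As a minor accompanying clarification in SAP 10.3.2.1, extend the third entry to read: *day is missing, and the month and year are those of first dose or later*. Keep the second entry. The list addresses only the start of the TEAE window; the 30-day upper limit in 9.3.16 continues to apply.

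The cost is two SAP sentences and about one line of derivation code. No data collection or protocol amendment is needed.
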